2.1 Background and rationale

Almost three million children and adolescents worldwide are living with HIV [1]. Every day, almost 1000 children and adolescents are newly infected and over 300 die from HIV/AIDS-related causes [1]. Eastern and Southern Africa are particularly affected, accounting for 65% of the epidemic in children and adolescents [1]. While substantial progress has been made towards providing antiretroviral therapy (ART) to all people living with HIV, which can suppress viral replication and prevent onward transmission of HIV [2–4], children and adolescents suffer high rates of treatment failure: among those younger than 15 years who receive ART, reported rates of treatment failure in Eastern and Southern Africa range from 10% (Eswatini) to over 50% (Eritrea, Mozambique, South Sudan) [5].

Treatment failure can be caused by non-adherence to therapy, viral drug resistance, or a combination of both, requiring differentiated clinical management. Without resistance testing, healthcare providers cannot definitively determine whether treatment failure is caused by drug resistance, necessitating an urgent switch of drug regimen, or non-adherence, in which case underlying causes must be addressed and unnecessary switching must be avoided to preserve the limited future treatment options.

Access to genotypic resistance testing (GRT) to detect viral drug resistance is lacking in most low-income settings [6]. As national HIV programs in sub-Saharan Africa struggle with limited resources, the question if resistance testing is of real clinical benefit or rather a “nice to have” is important as it impacts resource allocation within programs. The World Health Organisation (WHO) recommends resistance testing only upon confirmed treatment failure on second-line ART and/or protease-inhibitor-based ART, and even then only after a lengthy process of enhanced adherence counselling followed by a confirmatory viral load (VL) test [7].

A systematic review on the impact of genotypic and/or phenotypic resistance testing in ART-experienced individuals only found randomised clinical trials published before 2007, all conducted in Europe, the USA, or South America, only two of which included children and/or adolescents [8]. This review reported a potential slight reduction of virologic failure where resistance testing was available, but little or no difference in mortality, CD4 cell count, progression to AIDS, or adverse events. Among three modelling studies on the cost-effectiveness of GRT in southern Africa, published between 2011 and 2014, conclusions differed greatly [9–11].

The REVAMP trial did not observe a difference in viral suppression following clinical management informed by viral load versus genotypic resistance testing; however, this trial was conducted among adults taking NNRTI-based first-line ART and its results are thus not necessarily transferrable to children and adolescents taking newer ART regimens. A trial in Tanzania, including all age groups, implements GRT upon confirmation of treatment failure after enhanced adherence counselling [13]. Finally, the Opt4Kids trial assesses the impact of a combination of point-of-care VL testing and targeted resistance testing among children on first-line ART in Kenya [14].

2.2 Objectives

The primary research question is whether GRT improves clinical management and results in improved clinical outcomes – i.e. a higher proportion of participants who are alive, have no new clinical WHO stage 4 events¹ or HIV- or ART-related hospital admission, and are in care with a suppressed viral load – 9 months after randomisation.

We hypothesize that providing resistance information will allow for care to be customized according to the individual child/adolescent's health situation and needs, i.e. targeted adherence support for those without drug resistance and a rapid switch to an optimised ART regimen (with differentiated adherence support) for those with drug-resistant HIV, and thus lead to better clinical and virologic outcomes.

3. Study methods

3.1 Trial design

Full details of the trial are available in the current version (V 1.4) of the trial protocol as well as in summary version in the published protocol[2].

GIVE MOVE is an open-label, two-arm, multi-center, superiority randomised clinical trial conducted in Lesotho and Tanzania. Enrollment takes place in 10 sites (6 in Lesotho, 4 in Tanzania). Participants will be randomized in a 1:1 ratio to the intervention or the control arm. In the intervention arm, GRT (Sanger sequencing) will be performed. Based on the GRT and clinical information, an international expert committee issues a recommendation on the ART regimen and management. Taking this recommendation, the GRT as well as availability of drug formulations into account, the health care provider in charge of the

¹ WHO stage 4 events that are excluded: lymph node tuberculosis, stunting, oral or genital herpes simplex infection and oesophageal candidiasis

participant then takes the final decision on the composition of the ART regimen. Participants in the control arm will be managed according to the standard of care. Onward treatment will be informed by the follow-up VL in line with standard care and without performing resistance testing. The composite primary endpoint will be assessed 9 months (window: 32-44 weeks) after randomization (see Figure 1).

Although participants and treating healthcare professionals will not be blinded, laboratory technologists measuring the viral load (a key component of the primary and some secondary endpoints) will be blinded, as will the endpoint committee assessing if hospitalizations and potential WHO stage 4 events constitute an endpoint.

[figure not shown]

Figure 1: Overview of GIVE MOVE treatment algorithm and study visits. The decision follow-up visit is not shown. GRT: genotypic resistance testing; VL: viral load.

3.1.1 Eligibility

Eligibility criteria are as follows:

Inclusion criteria:

- In care in a study site
- Age ≥ 6 months and <19 years
- Latest HIV VL result ≥ 400 c/mL
- On an unchanged ART regimen for ≥ 6 months
- Phlebotomy for latest VL test <4 months before screening
- Consent given (see section 4.2)

Exclusion criteria:

- Indication for treatment switch according to WHO guidelines at screening
- 1st enhanced adherence counselling session initiated >2 weeks prior to screening
- Intention to transfer out of the study site (and not into a different study site) within 3 months after randomization
- Already enrolled in another study if judged as non-compatible by the (Local) Principal Investigator
- Pregnant or breastfeeding at screening (no exclusion based on pregnancy or breastfeeding after enrolment)
- Acute illness requiring hospitalization at screening (no exclusion based on hospitalization after enrolment)
- Received a resistance test within the last 12 months

3.1.2 Objectives and Endpoints

The trial objectives are:

Primary Objective: To assess if GRT-based management of viremia in CALHIV on ART in resource-limited settings improves overall health outcomes. The results of this trial are intended to inform future WHO and national guidelines on the use of GRT in CALHIV.

Secondary Objectives: To assess the impact of GRT-based management of viremia in CALHIV on various individual health outcomes including mortality, morbidity, and virologic status.

Exploratory Objectives: To assess the dynamics of viral resuppression and the viral development of drug resistance without vs with GRT-based management of viremia.

The primary and secondary endpoints of the trial are:

Primary endpoint

The trial is powered to detect a significant reduction of the composite primary endpoint in the intervention arm compared to the control arm. The composite primary outcome is comprised of: i) death due to any cause during the follow-up period (36 weeks), ii) HIV- or ART-related hospital admission of ≥ 24 hours duration (possibly, probably or definitely related to HIV or ART, judged by the endpoint committee blinded to the study arm) during the follow-up period (36 weeks), iii) new clinical WHO stage IV event (excluding lymph node tuberculosis, stunting, oral or genital herpes simplex infection and oesophageal candidiasis; judged by the endpoint committee blinded to the study arm) during the follow-up period (36 weeks), and iv) no documentation of a suppressed VL (<50 c/mL) at 9 months follow-up (window: 32-44 weeks).

The primary endpoint will be assessed as an event ratio of participants reaching any of the above-mentioned composite endpoints.

An endpoint committee whose members are unaware of study arm assignments will review all reported WHO stage IV events and hospitalizations and determine if the events in question qualify as endpoints.

Secondary endpoints

- Separate analyses of the four components of the primary endpoint, namely:
 - Death due to any cause
 - HIV- or ART-related hospital admission of ≥ 24 hours duration (possibly, probably or definitely related to HIV or ART, judged by the endpoint committee blinded to the study arm)
 - New clinical WHO stage IV event (excluding lymph node tuberculosis, stunting, oral or genital herpes simplex infection and oesophageal candidiasis, judged by the endpoint committee blinded to the study arm)
 - No documentation of a suppressed VL (<50 c/mL) at 9 months follow-up (window: 32-44 weeks)
- Loss to follow-up, defined as no documented clinic visit in the window period (32-44 weeks) of the 9-month study visit
- Observed virologic failure, defined as a VL ≥ 50 c/mL, at the 9-month study visit (window: 32-44 weeks) among participants who had a viral load result at the 9-month study visit
- Composite endpoint (see primary endpoint above) assessed at 6 months (window: 20-28 weeks) after the decision on the regimen for onward treatment (i.e. after the follow-up VL result in the control arm or a GRT result in the intervention arm should be available)

Exploratory endpoints

1. Time to viral resuppression (<50 c/mL; considering VL testing done with samples from the 3-, 6- and 9-month study visit in both arms)
2. Drug regimen switches in the absence of major drug resistance mutations and non-switches in the presence of major drug resistance mutations (as identified by Sanger sequencing, according to the Stanford HIV drug resistance database)
3. Emergence of new drug resistance mutations within the study period (i.e. measured drug resistance at the 9-month visit vs at the baseline visit)

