3.5 Statistical interim analyses and stopping guidance

One formal interim analysis is planned. The cut-off for this interim analysis is planned when 138 participants (50% of the intended sample size) have completed the 9-month study visit and/or reached the primary endpoint. The same analysis as planned for the final analysis will be performed for the composite primary endpoint. However, only stratification variables will be included in the analysis and no sensitivity analyses will be done.

The trial may be concluded early for success if a significant difference between the two trial arms for the composite primary endpoint is achieved at the time of the interim analysis. We will use the conservative Haybittle-Peto stopping level of $p=0.001$ [3].

In addition, premature stopping due to futility will be considered if obtaining a difference of ≥ 10 percentage points between the study arms is unlikely to be demonstrated. The trial will be stopped for inefficacy if the odds ratio is greater than 1 and the two-sided 95% confidence interval does not contain the alternative hypothesis (i.e., odds ratio of 0.57) [4].

The interim analysis will be performed by an external independent statistician at an external data analysis center, who will not be involved in the study conduct and will be blinded for the treatment allocation. The results will be reviewed by a Data Safety Monitoring Board, who will issue a recommendation to continue or stop the trial to the Steering Committee. The Steering Committee will vote on and thereby determine the continuation or termination of the trial. In the event of a tie, the Sponsor/Chief Investigator will cast the deciding vote.

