3.7 Timing of outcome assessments

Table 2 shows the timing of outcome assessments, the permitted ranges according to the protocol, and the ranges that will be used for analysis. The protocol provides all times in months and weeks. The lower and upper limits of the analysis windows correspond to the lower and upper protocol-defined limit, respectively.

If more than one value of the viral load outcome is collected during the analysis window, the first one in the analysis window will be used.

Table 2. Follow-up and permitted windows for endpoints.

Follow-up, months	Follow-up, weeks	Range according to the protocol, weeks	Analysis window, days
3	12	10 – 14	≥ 70 and < 98
6	24	20 – 28	≥ 140 and < 196
9	36	32 – 44	≥ 224 and < 308
9	44	Up until study completion*	< 308

4. Statistical principles

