5.3 Withdrawal/follow-up

The CONSORT flowchart will summarize enrolment, decision, 6, and 9-month study visit for each participant, by randomized group. Reasons will be given for participants who did not complete follow-up as expected.

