6.1 Outcome definitions

The VL of participants who did not have a VL measured for the primary and secondary endpoints within the required window will be considered as missing. This includes not having a visit within the respective window, visits without a blood draw, and blood draws with no result available. Missing VL will be counted as having achieved the primary endpoint, i.e. considered as an unsuppressed VL. Clarification of secondary and other outcome definitions are provided in section 3.1.2.

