Effect modification of the primary endpoint by country (Lesotho or Tanzania), gender (male or female), age ([\geq 6 months to <12 years] or [\geq 12 years to <19 years]), and ART regimen at enrolment (NNRTI-, PI-, or INSTI-based regimen) will be assessed by incorporating an interaction between arm and the effect modifier acknowledging that power will be low. Regimens at enrolment containing more than one of the above-mentioned ART types will be classified as INSTI-based if they contain at least one INSTI as well as one or more PI(s) and/or NNRTI(s), and as PI-based if they contain at least one PI and one or more NNRTI(s). If there are small numbers of participants within certain subgroups, then such an approach may not be feasible and instead we would restrict the model to the subgroups of sufficient size. If the interaction term is found to be significant, effect estimates will be summarized by subgroup. As the study is not powered for these pre-planned subgroup analyses, these results will be considered exploratory.

Secondary endpoints

For the secondary endpoints defined by the individual components of the composite outcome, we will summarize the number and proportion of participants meeting each endpoint definition as described in 3.1.2. We will follow the same approach as for the main primary outcome analysis if numbers allow, otherwise we will compare the endpoints between the study arms using a chi-squared or Fischer's exact test (in the case of limited events).

For the remaining secondary endpoints, we will follow the same approach as for the main primary outcome analysis if numbers allow. All analyses of secondary outcomes will be done on the mITT set.

Exploratory endpoints

If the number of events is sufficient, the exploratory endpoint of time to documented viral suppression will be assessed using Kaplan Meier estimation and Cox proportional hazard models adjusted for the stratification factors, reporting hazard ratios and 95% confidence intervals.

The exploratory endpoints of drug regimen switches and emergence of new drug resistance mutations will be compared between the study arms using a chi-squared or Fischer's exact test (in the case of limited events).

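### Loss to follow-up makes no exception for deaths, so a participant who dies before any visit in weeks 32-44 is counted as lost

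*SAP*

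**What the plan says.** Among the secondary endpoints in SAP section 3.1.2 is "Loss to follow-up, defined as no documented clinic visit in the window period (32-44 weeks) of the 9-month study visit". The absence of a documented visit is the only criterion.

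Death from any cause is component (i) of the primary composite, counted over 36 weeks. It is also a secondary endpoint of its own, under the item "Separate analyses of the four components of the primary endpoint, namely".

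Four other places bear on the definition:

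- Section 6.1 adds nothing to it and points back: "Clarification of secondary and other outcome definitions are provided in section 3.1.2".
- Section 6.2 sets the analysis: "For the remaining secondary endpoints, we will follow the same approach as for the main primary outcome analysis if numbers allow". That means adjusted logistic regression with an odds ratio and a risk difference. The same section puts all secondary analyses on the mITT set.
- Section 4.3 removes from the mITT set only participants found after randomisation to be ineligible. Section 6.3 includes everyone as randomised for the secondary outcomes, with virological failure as the only exception.
- Section 5.3 says of the CONSORT flowchart: "Reasons will be given for participants who did not complete follow-up as expected".

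**The concern.** Loss to follow-up is normally read as a measure of retention: participants whose status is unknown or who have left care. A participant known to have died is neither. As the endpoint is written, such a participant is an event for both death and loss to follow-up.

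If deaths differ between arms, the modelled comparison of loss to follow-up will differ too, even where surviving participants are retained equally well. The result could be reported as an effect of resistance testing on retention when it reflects mortality. The two outcomes are listed separately among the secondary endpoints, so a reader will expect them to measure different things.

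**Working it through.** **Is there an exception anywhere?** The definition in 3.1.2 has none, 6.1 refers back to it, and 4.3, 6.2 and 6.3 keep deaths in the analysis set. The next item in the 3.1.2 list, observed virologic failure, is expressly limited to participants with a viral load result. The SAP thus writes a restriction where it wants one. A programmer following the text would code as lost:

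- a participant who dies before week 32;
- a participant who dies inside the window before attending.

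A death after a documented window visit is not affected.

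**Arm size.** Table 1 in section 3.3 gives 138 per arm for 20% versus 35%. Section 3.5 agrees, placing the interim analysis "when 138 participants (50% of the intended sample size) have completed the 9-month study visit", so the total is 276 at 1:1 allocation. The figure reproduces with the pooled-variance chi-squared formula at two-sided 5% and 80% power:

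n = [1.960 × √(2 × 0.275 × 0.725) + 0.842 × √(0.20 × 0.80 + 0.35 × 0.65)]² / 0.15² = 137.9, rounded up to 138.

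The mITT set may be slightly smaller.

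**Effect of each death.** One death without a window visit adds 1/138 = 0.72 percentage points to its arm. Three add 3/138 = 2.17 points.

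**Illustration.** The SAP states no death or loss rate, so the counts below are assumptions. Let b participants be truly lost in each arm, and let one arm have extra deaths before a window visit, so that a = b + extra deaths. The crude odds ratio is [a/(138 − a)] / [b/(138 − b)].

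| True losses per arm (b) | One extra death | Three extra deaths |
|---|---|---|
| 5 | 6 vs 5: OR 1.21 | 8 vs 5: OR 1.64 |
| 10 | 11 vs 10: OR 1.11 | 13 vs 10: OR 1.33 |
| 20 | 21 vs 20: OR 1.06 | 23 vs 20: OR 1.18 |

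With deaths counted as non-events, each cell compares b with b among 138, and the odds ratio is 1.

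**Precision.** Crude 95% intervals are wide: 0.36 to 4.06 for 6 vs 5, 0.52 to 5.13 for 8 vs 5, 0.56 to 3.15 for 13 vs 10, and 0.61 to 2.26 for 23 vs 20.

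**Composition of the endpoint.** The share of deaths among those counted as lost is d/(l + d), with d the death rate and l the true loss rate. For an assumed l of 5% and d of 1%, 2%, 3% or 5%, the share is 17%, 29%, 38% or 50%. For l of 10% it is 9%, 17%, 23% or 33%.

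**Timing.** In Table 2 of section 3.7 the 9-month window runs from day 224 to before day 308, which is 84 days. The 36-week limit on the death component falls at 36 × 7 = day 252. So 308 − 252 = 56 of the 84 days (67%) lie after it. The last row of Table 2, labelled "Up until study completion", does not say whether it extends that limit. A corrected definition has to place deaths in this interval as well.

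**The case against.** The endpoint can be read as not being seen at nine months for any reason. That suits a trial whose idea of success is being alive and in care, and it avoids treating death as a competing event. The secondary endpoints overlap in any case: a participant who dies before a viral load sample in the window also counts as having no documented suppression. Deaths are tabulated separately and the flowchart gives reasons, so a reader could largely separate the counts. The wide intervals above show that a few deaths would not by themselves support a claim about retention.

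Most of this limits the size of the point. It does not remove it. An all-cause non-attendance measure is a legitimate endpoint, but the SAP calls it loss to follow-up. The flowchart and the separate death count are descriptive and leave the modelled odds ratio and risk difference as they are.

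Two further remarks stand. The definition is equally silent on known withdrawals and transfers out. And excluding deaths has a cost of its own: it lowers the apparent loss in the arm with more deaths, and it moves to the death category a participant who left care early and died later.

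**Conclusion.** The concern holds and is minor. Followed literally, the SAP counts every participant who dies without a documented visit in weeks 32-44 as lost to follow-up, and models that mixture as one outcome. The distortion is 0.72 percentage points per death in an arm of 138. Its effect on the odds ratio depends on how many participants are truly lost: the fewer they are, the larger the effect. The illustrative odds ratios rest on assumed counts, since the SAP gives no rates. Only this secondary endpoint is affected. In the primary composite, a death within 36 weeks and a missing viral load are both events, and loss to follow-up plays no part in the sample size.

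**What to change.** In section 3.1.2, define loss to follow-up as no documented clinic visit on day ≥224 and <308 in a participant not known to have died before day 308. State that known deaths stay in the mITT denominator as non-events. State in the same edit how known withdrawals and transfers out are classified.

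Report by arm three mutually exclusive categories that add up to the mITT number:

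1. visit in the window;
2. died before day 308 without a window visit;
3. lost to follow-up.

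Within the second category, show deaths on days 252-307 separately. Every non-attender then has exactly one place, whichever way the 36-week limit and the last row of Table 2 are read.

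Present the second and third categories side by side, because a lower loss rate in an arm with more deaths must not be read as better retention. Their sum is the endpoint as now written, so that figure remains available.

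The cost is one line of definition, one split table row and a few lines of derivation code. Visit dates and deaths are already needed for other endpoints. The change should be made before outcome data are seen by arm.

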3.2 Randomization

Certain baseline factors may have an effect on the primary and secondary endpoints, including the site, age, gender, and the participant's ART regimen at enrolment. In order to minimise bias, randomisation was stratified by:

- Country (Lesotho or Tanzania)
- Age at enrollment ([≥ 6 months to <12 years] vs [≥ 12 years to <19 years])
- ART regimen at enrolment (NNRTI-based, protease inhibitor (PI)-based, or integrase strand transfer inhibitor (INSTI)-based regimen)

In children, gender is unlikely to have a major impact on outcomes. Given the sample size and the relatively even gender distribution (expected female to male ratio approximately

3:2), a strong clustering effect is unlikely. However, gender will be considered in the planned subgroup analysis.

Eligible and consented patients are consecutively enrolled and randomised in a 1:1 ratio to the intervention and control arms. Randomisation is stratified according to the factors listed above, using permuted blocks with varying block size. Randomisation is automated using the MACRO electronic data capture software (Elsevier; see chapters 4.3 Study procedures, and 8.2 Data recording and source data). Randomisation of a participant is performed once eligibility and consent have been confirmed and entered into the database, thereby maintaining concealment of allocation.

